7.2.4. Visit and Assessment Changes Due to COVID-19

Changes in scheduled visits and corresponding assessments due to COVID-19 restrictions will be captured as in the eCRF. In the eCRF completion guidelines, sites were provided instructions for capturing visits that were missed (not performed) or performed remotely. The following visit and assessment changes will be included in submission datasets:

- All on-site visits that were converted to remote visits for any reason will be flagged. This information will be captured in the eCRF and protocol deviation log.
- Missed visits are flagged if the "not done" field is indicated and the reason for "not done" is indicated as "Covid-19 restriction" or "Participant acquired Covid-19" from the dropdown list.

7.2.5. Missing and Partial Data

Missing or partially missing start and stop dates for concomitant medications and AEs will be imputed as described in Appendix 1: Date Imputation Rules. However, imputed dates will NOT be presented in the listings as their sole purpose will be for the classification of the medications as past, concomitant or post (refer to Section 8.5).

Missing data will be handled as described below:

 Missing safety data will not be imputed except for the start and stop dates for AEs and concomitant medication.

- Missing data for primary estimand and key secondary estimand will be handled as described in Section 9.1 and 9.2.
- Missing data for other secondary endpoints, and exploratory endpoints will be managed as described in Section 9.2 and 9.3.
- To manage the partial missing scales on TETRAS composite outcome score (derived using TETRAS-ADL and TETRAS-PS items as described in Section 9.1.1), the imputation of missing ADL and PS scores will be handled separately. For the purposes of this imputation, only ADL items 1 to 11 and PS items 6 and 7 are considered. Additionally, item 6 of the PS includes 2 separate scores (for the left- and right-hand responses).
 - o If \leq 3 ADL item scores are missing at a specific time point, the mean of the remaining nonmissing ADL item scores at that time point will be used to impute the missing ADL item score value. The TETRAS composite outcome score will then be calculated as the sum of the observed and imputed item scores. If \geq 4 ADL item scores are missing, the composite outcome score will not be calculated.
 - o If 1 PS item score is missing at a specific time point, the mean of the remaining non-missing PS item scores at that time point will be used to impute the missing PS item score value. The TETRAS composite outcome score will then be calculated as the sum of the observed and imputed item scores. If \geq 2 PS item scores are missing, the composite outcome score will not be calculated.

7.3. Hypotheses Testing

The null and alternative hypotheses for analysis of the primary estimand are:

H1_0: $\mu_{(JZP385)} = \mu_{(Placebo)}$ (i.e., there is no difference in the mean change on the TETRAS composite outcome score from Baseline to Week 12 between each JZP385 dose group and the placebo group).

H1_A: $\mu_{(JZP385)} \neq \mu_{(Placebo)}$ (i.e., the mean change on the TETRAS composite outcome score from Baseline to Week 12 is not equal between each JZP385 dose group and the placebo group).

The null and alternative hypotheses for analysis of key secondary estimand are:

H2_0: $\pi_{(JZP385)} = \pi_{(Placebo)}$ (i.e., there is no difference in the proportion of participants who improved [\geq 1 point decrease] on the CGI-S from Baseline to Week 12 between each JZP385 dose group and the placebo group.

H2_A: $\pi_{(JZP385)} \neq \pi_{(Placebo)}$ (i.e., there is a difference in the proportion of participants who improved [\geq 1 point decrease] on the CGI-S from Baseline to Week 12 between each JZP385 dose group and the placebo group).

Each JZP385 treatment group will be compared individually to the placebo group in the order specified in Section 7.4.

7.4. Level of Significance & Multiplicity Adjustment

To evaluate the efficacy of JZP385 at doses of 10, 20, and 30 mg/day compared with placebo, pairwise treatment difference between each of the 3 doses and placebo will be tested at the end of Week 12 for the primary and key secondary endpoints.

The family-wise Type I error rate will be controlled at a 2-sided significance level of 0.05. To address the multiplicity issue due to the multiple efficacy endpoints and doses, a fixed hierarchical testing sequence will be employed. The testing procedure will stop when a p-value exceeds 2-sided significance level of 0.05 (see below).

Statistical hypotheses to be tested (in sequential order):

- 1. Change in the TETRAS composite outcome score from Baseline to Week 12, 30 mg/day versus placebo.
- 2. Difference in proportion of participants who improved (≥ 1 point decrease) on the CGI-S from Baseline to Week 12, 30 mg/day versus placebo.
- 3. Change in the TETRAS composite outcome score from Baseline to Week 12, 20 mg/day versus placebo.
- 4. Difference in proportion of participants who improved (≥ 1 point decrease) on the CGI-S from Baseline to Week 12, 20 mg/day versus placebo.
- 5. Change in the TETRAS composite outcome score from Baseline to Week 12, 10 mg/day versus placebo.
- 6. Difference in proportion of participants who improved (≥ 1 point decrease) on the CGI-S from Baseline to Week 12, 10 mg/day versus placebo.

7.5. Subgroups and Subgroup Analyses

Subgroup analyses will be conducted on the primary and key secondary efficacy endpoints for the following:

- Sex at birth (Female, Male)
- Region (North America, Europe)
- High enrolling sites, based on the number randomized (≥ 20 randomized, < 20 randomized)
- Randomization stratum: TETRAS composite outcome score ($\leq 17, > 17$)
- Randomization stratum: antitremor medication (No. Yes)
- Age $(< 65, \ge 65)$
- Diagnosis (ET, ET plus)
- Family history of ET (No, Yes)

The output for estimating the treatment difference within subgroup will not be provided (least square means, standard error, LS Mean Difference (95% CI) or proportion difference (95% CI) and p-value) if the data are too sparse.

It should be noted that the study was not designed to detect treatment differences with high statistical power within any subgroups.

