9. STATISTICAL CONSIDERATIONS

9.1. Statistical Hypotheses

The null and alternative hypotheses for analysis of the primary estimand variable are:

 H_0 : $u_{JZP385} = u_{Placebo}$

 H_1 : $u_{JZP385} \neq u_{Placebo}$

Specifically, the null hypothesis states that there is no difference in the mean change on the TETRAS composite outcome score from Baseline to Week 12 between each dose of JZP385 and the placebo control group. The alternative hypothesis is that the mean change on the TETRAS composite outcome score from Baseline to Week 12 is not equal between each dose of JZP385 and the placebo control group.

The null and alternative hypotheses for analysis of the key secondary estimand variable are:

 H_0 : $p_{JZP385} = p_{Placebo}$

 H_1 : p JZP385 \neq p Placebo

Specifically, the null hypothesis states that there is no difference in the proportion of participants who improved by ≥ 1 point on the CGI-S from Baseline to Week 12 between each dose of JZP385 and the placebo control group. The alternative hypothesis is that the proportion of participants who improved by ≥ 1 point on the CGI-S from Baseline to Week 12 is not equal between each dose of JZP385 and the placebo control group.

Each JZP385 treatment group will be compared individually to placebo. The remaining secondary and exploratory endpoints will not be controlled within the formal hypothesis test for type I error. All safety analyses will be descriptive; no formal statistical testing will be performed.

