5.3. Power and Sample Size Calculations

A sample size of 80 evaluable participants per treatment group will provide 90% power to detect a difference of 3.1 points for the change from Baseline to Week 12 on the TETRAS composite outcome between JZP385 and placebo, with a common SD of 6.0 points. This sample size will also provide 91.7% power to detect a 26% between-treatment (assuming JZP385 at 66% versus placebo at 40%) difference in proportion of participants who improved by at least 1 point on the CGI-S from Baseline to Week 12. Assuming a 20% dropout rate, a total of 400 participants (100 participants per treatment group) will be randomized. The sample size calculation for the TETRAS composite outcome score is based on t-test and the CGI-S sample size calculation is based on chi-square test, both tests are 2-sided at the significance level of 0.05.

For the TETRAS composite outcome, at least 80% power is still achieved if there is a reduction of 0.4 points from the assumption in the difference in mean change from baseline (assuming a constant common standard deviation) or an increase in common standard deviation by 1 point, (assuming a constant difference in means). For the key secondary endpoint, at least 80% power is still achieved with comparable shifts in the assumptions.

The assumptions for these sample sizes were supported by the results from the Phase 2 study in Essential Tremor (Study CX-8998-CLN2-001 [T-CALM]), where the TETRAS ADL and PS were assessed. Using the same derived TETRAS composite outcome score, as defined in this SAP, and assessing the change from baseline to Day 28 in T-CALM, there was a difference in means between JZP385 and placebo of 3.04 and a difference in LS Means of 3.27. The standard deviation for the change from baseline was 5.86 in JZP385 and 5.47 in placebo. It is hypothesized that the treatment improvement will remain consistent over the longer study duration of JZP385-201, with a small increase in variability, thus supporting the above assumptions.

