9.1.5. Subgroup Analyses

Subgroup analyses for groups specified in Section 7.5 will be performed for the primary efficacy estimand using the ITT Analysis Set. The primary analysis in Section 9.1.2 will be used for the subgroup analyses. However, the randomization stratification factor will be removed from the model for the analysis by subgroups of participants by randomization strata. The corresponding parametric analysis used for the overall sample will be applied to each subgroup. A forest plot summarizing the treatment difference and 95% CI will be provided for each subgroup with sufficient sample size.

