9.2.5. Subgroup Analyses

Subgroup analyses for groups specified in Section 7.5 will be performed for the key secondary efficacy estimand using ITT. The analysis in Section 9.2.2 will be used for the subgroup analyses. However, the randomization stratification factor will be removed from the model for the analysis by subgroups of participants by randomization strata.

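### SAP 7.5 plans up to 96 unadjusted within-subgroup p-values but no treatment-by-subgroup contrast, so it never tests whether the effect differs between subgroup levels

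*SAP*

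**What the plan says.** SAP 7.5 opens: "Subgroup analyses will be conducted on the primary and key secondary efficacy endpoints for the following". The eight factors are sex, region, site size, baseline TETRAS stratum, antitremor-medication stratum, age, diagnosis and family history, each with two levels. The listed within-level output is the LS means and their standard errors, then "LS Mean Difference (95% CI) or proportion difference (95% CI) and p-value) if the data are too sparse"; sparseness is the only reason given for withholding it, and no threshold is set.

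The methods repeat the main analyses level by level. SAP 9.1.5: "The primary analysis in Section 9.1.2 will be used for the subgroup analyses". SAP 9.2.5: "The analysis in Section 9.2.2 will be used for the subgroup analyses". A forest plot of differences with 95% CIs is planned for the primary endpoint.

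Interactions appear in SAP 9.1.2 and 9.2.6.2 (with week) and 9.3.3 (with time point). None involves a subgroup. Protocol 9.4.2 also announces subgroup analyses without an interaction term and leaves the details to the SAP.

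On error control, SAP 7.4 says "The family-wise Type I error rate will be controlled at a 2-sided significance level of 0.05" and lists six overall hypotheses. Protocol 9.1 adds "The remaining secondary and exploratory endpoints will not be controlled within the formal hypothesis test for type I error", which does not mention subgroup results on the two confirmatory endpoints. SAP 7.5 ends with a caution about low power within subgroups.

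**The concern.** A subgroup table is read to learn whether the effect differs between, say, participants who do and do not take antitremor medication. A p-value against placebo in each level does not answer that. One level can fall below 0.05 and the other above it when the two effects are almost the same.

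With this many p-values, two misreadings become likely. If the drug is inactive, some level will probably look significant for some dose. If the drug works equally in everyone, some level will probably look unresponsive. The primary and key secondary conclusions are not at stake. What is at stake is how readers interpret the subgroup tables, for example when they consider population or dose for later work.

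**Working it through.** **1. The plan's own figure.** SAP 5.3 states: "A sample size of 80 evaluable participants per treatment group will provide 90% power". The assumed treatment difference on the TETRAS composite is 3.1 points, with SD 6.0 and a two-sided 0.05 t-test. The standard error is 6.0 x sqrt(2/80) = 0.949, and 3.1/0.949 = 3.27. The noncentral t gives 90.1%, which agrees. The CGI-S figure (66% v 40%, pooled chi-square) comes out at 91.66% against the stated 91.7%.

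**2. Count.** 8 factors x 2 levels = 16. With 3 doses that is 48 p-values per endpoint, and with 2 endpoints 96. This is a ceiling, since sparse levels may be dropped.

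**3. If the drug does nothing.** The expected number of nominal hits is 96 x 0.05 = 4.8. Independence would give 1 - 0.95^96 = 0.993, but the tests share a placebo arm, participants and correlated endpoints. A simulation is therefore needed. Its settings are:
- 80 or 100 per arm, eight independent factors split 50/50 or 30/70, 40% CGI-S responders and endpoint correlation 0 to 0.8;
- unadjusted t-tests and pooled z-tests;
- splits, independence of factors and endpoint correlation are assumptions, as the documents give none of them.

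| Chance of at least one nominal two-sided p<0.05 | Any direction | Favouring JZP385 |
|---|---|---|
| 48 primary-endpoint tests | about 0.69-0.73 | about 0.37-0.42 |
| All 96 tests | about 0.87-0.92 | about 0.53-0.65 |

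A latent correlation of 0.3 between factors leaves the any-direction figure for 96 tests at 0.87-0.90.

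**4. If the planned effect holds in everyone** (3.1 points, SD 6.0, 80 per arm, unadjusted t-test):
- Half-size level, 40 per arm: SE = 6.0 x sqrt(2/40) = 1.342; 3.1/1.342 = 2.31; power 63%.
- 30% level, 24 per arm: SE = 6.0 x sqrt(2/24) = 1.732; 3.1/1.732 = 1.79; power 42%.

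For one dose on the primary endpoint, at least one of the 16 levels is then non-significant with simulated probability of about 0.88 (50/50 splits) to 0.97 (30/70 splits).

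**5. Why two p-values do not make a comparison.** Take, as an illustration, two half-size levels with estimates 3.1 and 2.4, each with SE 1.342. The t values are 2.31 (p about 0.02) and 1.79 (p about 0.08), so one level is significant and the other is not. The difference is 0.7 with SE 6.0 x sqrt(4/40) = 1.897, so z = 0.37 and p is about 0.71. The data give no sign that the effects differ.

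**6. What the contrast can and cannot do.** With 40 per arm in each level and a true difference of a full 3.1 points between levels, 3.1/1.897 = 1.63. Power is about Phi(1.63 - 1.96) = 37%. Under the null, 48 dose-by-dose contrasts (8 factors x 3 doses x 2 endpoints) give a simulated chance of 0.86-0.90 of at least one nominal hit.

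**The case against.** Several points on the other side stand:
- SAP 7.5 warns that the study lacks high power within subgroups. That is a fair caution against reading a non-significant level as no effect. It does not cover chance positives, or inferring a difference from significant here and not there.
- The 96 is a maximum, and no document states a threshold or decision rule for subgroup p-values.
- The any-direction figure includes results favouring placebo. A result that might tempt someone to pick a subgroup is less likely (0.53-0.65).
- The power figures use unadjusted t-tests. The planned MMRM adjusts for baseline and runs on ITT, so actual subgroup power may differ.
- Keeping the within-level 95% CIs keeps nearly the same information as the p-values, and the contrasts add their own chance hits. The fix supplies the right comparison; it does not abolish chance findings.
- Protocol 9.4.1.3 does describe pooling by region or country as exploratory, but that covers no other factor.
- Neither document says that subgroup p-values will drive a dose or population choice.

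A reader might also infer that the stated 0.05 is exceeded 14 to 18 times (0.70/0.05 and 0.90/0.05). The documents do not support that. The 0.05 in SAP 7.4 belongs to six listed hypotheses, no subgroup test is among them, and no subgroup p-value can support a confirmatory claim under the plan.

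**Conclusion.** The gap is real: within-level p-values are planned, and a test or estimate of the difference between levels is not. It is a problem of interpretation, with no effect on the confirmatory results. Calling a false subgroup hit close to certain would go too far: about nine in ten in either direction, and somewhat over one in two in favour of JZP385, is what the calculation supports. A spurious non-significant level under a uniform effect is likely, and the low-power sentence answers that only in part. These probabilities rest on the assumed splits, factor independence, endpoint correlation and unadjusted tests. The absence of a between-level comparison rests on the text alone. The change is inexpensive and worth making.

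**What to change.** In SAP 7.5, 9.1.5 and 9.2.5:
1. For each factor, fit one MMRM to all ITT participants, adding subgroup, treatment-by-subgroup, subgroup-by-week and treatment-by-subgroup-by-week terms to the SAP 9.1.2 model. For each dose, report the Week 12 difference between the two levels' effects with its 95% CI.
2. For CGI-S, report for each dose the difference between the two levels' risk differences with its 95% CI, pooled over the imputations.
3. Keep the within-level estimates, 95% CIs and forest plot. Drop the within-level p-values.
4. State that all subgroup results, including these contrasts, are exploratory, lie outside the SAP 7.4 family and support no claim of efficacy or of its absence in a subgroup.

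No new data are needed. The cost is eight additional MMRMs, the matching CGI-S contrasts and SAP wording, best settled before unblinding. If that point has passed, SAP 3 lets the change be documented with its rationale in the study report. The contrasts have low power and carry an unadjusted chance of a nominal hit, so they should be presented as descriptive.

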7.6. Changes to Planned Analyses

Section 9.4.1.4 of the Protocol outlines the approach to imputation of missing item scores, as part of the TETRAS composite outcome score. Based on these rules, it was possible for a participant to have a missing TETRAS PS score at a visit and still have a valid composite outcome score. The rules have been amended to change the imputation of missing item scores to be managed within the individual subscale scores (ADL or PS) before the composite outcome score is calculated. The details of the new calculation are specified in Section 7.2.5.

The mITT Analysis Set defined in the Protocol Section 9.3 has been updated to ITT, to include all randomized participants for the primary efficacy analyses.

For Adverse Events of Special Interests defined in Protocol Section 8.4.6, presyncope was removed in the formal definition of AEOSI in Section 10.2.1.

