8.4.6. Adverse Events of Special Interest and Other Reportable Experiences

The AEOSIs defined for this study are based on observations from the phase 1 and 2 studies that have been conducted with JZP385 to date and consist of the following: hallucinations of any type and syncope (including presyncope).

Additional information regarding the reporting of AEOSIs is provided in Appendix 4.

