- The SAE Reporting Form should be completed as much as possible before transmittal.
- Contacts for SAE reporting can be found in the Trial Site Binder.

Reporting of AEOSIs and OREs

Reporting of AEOSIs and OREs to the sponsor or designee

- AEOSIs and OREs must be reported to the sponsor or its designee using an ORE/AEOSI Reporting Form within 24 hours of first knowledge of the event by study personnel.
- The form, instructions on completion and contact information can be found in the Trial Site Binder.
- The ORE/AEOSI Reporting Form should be completed as much as possible before transmittal.
- Contacts for ORE/AEOSI reporting can be found in the Trial Site Binder.

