10.2.1. Adverse Events of Special Interest

TEAEs of special interest will be summarized and may include the terms or categories noted below.

- Hallucinations of any type
- Syncope

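### SAP 7.6 and 10.2.1 drop presyncope from the protocol's AEOSI without a reason, so no planned output counts the participants per arm with syncope or presyncope

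*SAP*

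**What the plan says.** Protocol 8.4.6 names two AEOSIs: "hallucinations of any type and syncope (including presyncope". It gives the source of the list: "The AEOSIs defined for this study are based on observations from the phase 1 and 2 studies" of JZP385. Protocol Appendix 4, under the reporting of AEOSIs and other reportable experiences, sets the site's duty: "AEOSIs and OREs must be reported to the sponsor or its designee using an ORE/AEOSI Reporting Form within 24 hours" of first learning of the event. Read with 8.4.6, that duty covers presyncope.

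SAP 7.6, which lists the changes from the protocol's planned analyses, says that "presyncope was removed in the formal definition of AEOSI in Section 10.2.1". SAP 10.2.1 then introduces its list with "TEAEs of special interest will be summarized and may include the terms or categories noted below" and gives two entries: hallucinations of any type, and syncope. SAP 10.2 takes both the AEOSI incidence table (by category and preferred term) and the AEOSI listing from the 10.2.1 definition.

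The same SAP section explains its other two changes. The new item-imputation rule is needed because under the old one "it was possible for a participant to have a missing TETRAS PS score at a visit and still have a valid composite outcome score". The move from mITT to ITT is made so that all randomized participants enter the primary efficacy analyses. Only the safety change has no explanation.

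**The concern.** The protocol and the SAP use the same label for two different sets of events. Through the trial, sites send presyncope to the sponsor on an AEOSI form. At analysis, the AEOSI table and listing will not contain it, so a reader who compares the forms with the table cannot make them agree and finds no reason in the SAP.

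The protocol treats this area as worth watching. Section 2.3.1 lists orthostatic hypotension among the things to be monitored, exclusion criterion 20 screens for it, and SAP Table 6 has markedly abnormal criteria for orthostatic blood pressure and pulse. There is no Data Monitoring Committee (Protocol 10.1.5) and all safety analysis is descriptive (Protocol 9.4.5), so the way events are grouped in the tables carries much of the interpretation. What is at stake is one grouped safety count, by arm, across three doses and placebo.

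The permissive verb in SAP 10.2.1 adds a smaller problem: even the shortened list is not fixed.

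**Working it through.** The plan states no figure on this point, so there is none to reproduce. The check is a comparison of texts, followed by an illustration under assumed rates.

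**1. Definitions side by side**

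| | Protocol 8.4.6 | SAP 10.2.1 |
|---|---|---|
| Hallucinations of any type | yes | yes |
| Syncope | yes | yes |
| Presyncope | yes | no |
| Wording of the list | definite | permissive |

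**2. Where a treatment-emergent presyncope event would appear under SAP 10.2**

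- AEOSI table by category and preferred term: no.
- AEOSI listing: no.
- TEAE tables by SOC and preferred term, and by preferred term alone: yes, as its own term.
- Tables by maximum severity and by time of first onset: yes.
- Listing of all adverse events: yes.

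**3. Can the combined count be read from the general tables?** SAP 10.2 counts a participant once within each term. Let *a* participants in an arm have syncope and *b* have presyncope. The number with either lies between max(*a*, *b*), when the smaller group lies wholly inside the larger, and *a* + *b*, when nobody has both. With assumed counts *a* = 1 and *b* = 2 it is 2 or 3. The tables do not fix the number. An SOC total does not help, because it takes in every other term in its class. The count could be built by hand from the listing of all adverse events, but it is not a planned output.

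**4. Illustrative size.** Let *r* be the ratio of participants with presyncope to participants with syncope, and assume that nobody has both. The share of affected participants left out of the SAP category is *r*/(1 + *r*). Arm size is 100 (Protocol 9.2). The syncope rate of 1% is an assumption. The chance of at least one event in an arm is 1 − (1 − *p*)^100, where *p* = 1% × (1 + *r*).

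| *r* | Share left out | *p*, combined | Chance of ≥ 1 event per arm |
|---|---|---|---|
| 0 | 0% | 1.0% | 63.4% |
| 0.5 | 0.5/1.5 = 33% | 1.5% | 77.9% |
| 1 | 1/2 = 50% | 2.0% | 86.7% |
| 2 | 2/3 = 67% | 3.0% | 95.2% |
| 4 | 4/5 = 80% | 5.0% | 99.4% |

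If syncope is instead assumed at 0.5%, the chance is 39.4% for syncope alone and 52.9% to 92.0% for the combined category over *r* = 0.5 to 4. At 2% it is 86.7% alone and 95.2% to nearly 100% combined. The share left out depends only on *r*. If some participants have both events, that share is smaller, since only those with presyncope alone are missed.

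**5. Effect on the design figures.** Safety is not tested formally and the AEOSI category enters no hypothesis in SAP 7.4. Sample size, power and type I error are unchanged.

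**The case against.** The strongest reply is that little is hidden. The change is declared in the section meant for such changes. Sites still collect presyncope and report it within 24 hours. It still appears by arm in the general TEAE tables, and orthostatic vital signs are tabulated separately. Protocol 9.4.5 lists the planned adverse event summaries and plans no AEOSI table; that table first appears in the SAP, so the protocol's definition served expedited reporting and no protocol-planned table was cut down. All of this stands, and it limits the point to the AEOSI table, the AEOSI listing and the combined count.

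Three stronger readings are tempting, and the documents support none of them.

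- A reader might infer that presyncope is the commoner form of the signal, or that syncope alone will be rare. Neither document gives a rate for either event. The first inference needs *r* above 1, and *r* is unknown.
- A reader might infer that the category was narrowed after data collection or with knowledge of results. The SAP is dated 31 May 2024, but no date is given for the end of data collection. SAP 4.2.1 speaks of a blinded medication review still to be done before database lock, SAP 8.2 allows for ongoing participants, and Protocol 9.4 permits the SAP to be finalised up to lock.
- A reader might infer from the illustration that a dose pattern would be missed. The chance of at least one event in a single arm does not measure how well arms can be told apart: a placebo arm at 3% would also give 95.2%.

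Nor do the documents link the permitted antitremor medication to syncope, so the point does not rest on that.

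**Conclusion.** The point holds as a mismatch of definitions with a specific reporting loss. Presyncope is part of an AEOSI in the protocol and is expedited by sites as such; the SAP removes it without a reason. The AEOSI table and listing will therefore not match the events reported as AEOSIs, and no planned output gives the number of participants per arm with syncope or presyncope.

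The size is unknown. Over assumed ratios from 0 to 4, between none and 80% of affected participants would fall outside the SAP category, assuming no participant has both events. These are illustrations and not estimates. No efficacy conclusion depends on the change. It deserves correction because the remedy is nearly free and needs no new data.

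**What to change.** In SAP 10.2.1, restore the protocol category, syncope including presyncope, for both the AEOSI table and the AEOSI listing. Give a combined participant count by arm, counting each participant once, with separate preferred-term rows for syncope and presyncope beneath it so that syncope alone stays visible. Delete the matching sentence in SAP 7.6. In the lead-in to the list, change *may include* to *include*.

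If the sponsor prefers the narrower definition, state the reason in 7.6 and still report the combined count by arm, for example as a line under the AEOSI table.

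The cost is a few words of SAP text and one extra row. The one real downside is that the AEOSI count will be higher if any participant has presyncope without syncope; the separate rows show where the increase comes from.
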